#### 6.2.4 Dose Limiting Toxicities

DLTs will be used to determine dose escalation, dose de-escalation, and the MTD (if reached), using the National Cancer Institute (NCI)-Common Terminology Criteria for Adverse Events Version 4.03 (CTCAE 4.03).

DLTs are defined as any Grade  $\geq 3$  AEs and irAEs, during treatment of either M4112 as single agent **CCI** by the Investigator and/or the Sponsor, during Cycle 1 at any dose level:

- Any Grade  $\geq 3$  nonhematological AE or irAE assessed by the Investigator or Sponsor during the first Cycle (first 28 days) of study treatment **except**:
  - Diarrhea of  $\leq 6$  days duration following adequate and optimal therapy that resolves to Grade  $\leq 1$
  - Grade 3 skin toxicity that resolves to Grade 1 or less with supportive measures within 7 days
  - Nausea and vomiting of  $\leq 72$  h duration with adequate and optimal therapy
  - Single laboratory values out of the normal range that have no clinical correlate, and resolve to Grade  $\leq 2$  within 6 days with adequate medical management (except Grade  $\geq 3$  liver function test increase without any clinical correlate)

- e. Grade 3 infusion-related reactions resolving within 6 h from the end of infusion and controlled with medical management
- f. Transient ( $\leq 72$  h) Grade 3 fatigue, local reactions, flu-like symptoms, fever, headache that resolves to Grade  $\leq 1$  with adequate treatment
- g. Keratoacanthoma and SCC of the skin. Any suspicious skin lesion that is local and should be resected with negative resection margin
- h. Symptomatic thyroid dysfunction which is manageable with adequate treatment and resolves to Grade 2 within 6 days
- i. Tumor flare phenomenon defined as local pain, irritation, or rash localized at sites of known or suspected tumor that resolve to Grade 2 within 6 days
- j. Asymptomatic Grade  $\geq 3$  lipase or amylase elevation not associated with clinical manifestations of pancreatitis.
- Any TEAE observed in subsequent cycle that in the opinion of the SMC needs to be taken into account for the overall evaluation of the safety and proposal of dose escalation
- Any Grade 4 neutropenia of  $> 5$  days duration, Grade  $\geq 3$  febrile neutropenia
- Grade 3 hemoglobin decrease ( $< 8.0$  g/dL) despite blood transfusion or erythroid growth factor
- Grade 4 hemoglobin decrease assessed as related to study drug
- Any Grade 4 thrombocytopenia or Grade 3 thrombocytopenia with bleeding
- Any Grade  $\geq 3$  clinical signs and symptoms related to increased QTc
- Evidence of hepatocellular toxicity attributable to study drug, such as increase in AST or ALT  $\geq 5$ -fold ULN for at least or  $\geq 3 \times$  ULN elevation of ALT or AST and elevation of serum total bilirubin to  $\geq 2 \times$  ULN, without initial findings of cholestasis (elevated serum ALP) or other apparent clinical causality (eg, viral hepatitis A, B, C, or co-medication).

If the above criteria are met, subjects should undergo close observation, including monitoring for symptoms (clinical signs of hepatitis, hypersensitivity, fatigue, decreased appetite, nausea, vomiting, abdominal pain, jaundice, fever, or rash) and hepatic function (AST, ALT, ALP and fractionated bilirubin) at least every 3 days, until symptoms and/or hepatic function abnormalities resolve, stabilize or return to baseline values. This event should be reported to the Sponsor within 24 h of learning of its occurrence.

Subjects experiencing DLTs during the DLT observation period (applicable for Part I only) as described in Section 6.2.4 will not receive further protocol therapy. Subjects with nausea and vomiting will maintain normal schedule without re-dosing.

In addition, any immune-related toxicity event observed in the next cycle will be reviewed and taken into account by the SMC for the overall evaluation of the safety and proposal of dose escalation of M4112 **CCI**.

All subjects treated in dose escalation cohorts who miss > 5 planned total daily doses of M4112 **CCI** in the first cycle (first 28 days) of the dose escalation part for other than safety reasons are not eligible for DLT assessment, will not be considered in the Bayesian model, and will not formally be replaced.

The MTD is defined by the SMC. An MTD is suggested from the Bayesian logistic regression model with target toxicity of 30%.

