**The following potential risks of M4112 are**

1. Gastrointestinal intolerance including ulceration, bleeding with anemia and inflammation of gastric mucosa.
2. Liver toxicity either due to liver hypertrophy or direct liver lesions.
3. QT/QTc prolongation.
4. Inhibition/autoinduction of CYP3A4.
5. irAEs/autoimmune disorders.

Gastro-intolerance including ulceration and inflammation of gastric mucosa is a potential risk for M4112. The symptoms of gastrointestinal intolerance (nausea, vomiting, and diarrhea etc.) will be closely monitored, reported, and investigated. Discontinuation/interruption of treatment will be recommended for higher grade (Grade  $\geq 3$ ) events.

Liver toxicity is the clinically significant potential risk and relates to findings in animal toxicity studies. Subjects must be screened for potential impaired liver function or liver disease prior to treatment with a detailed medical history and clinical examination. All subjects enrolled in the clinical study should be counseled for early recognition and reporting of drug-related liver disease, and should be closely monitored in case of increased liver function tests and bilirubin (see Section 6.2.3).

QT/QTc prolongation is another important potential risk for M4112. A detailed medical history and medical examination to rule out a pre-existing heart disease and history of QT/QTc prolongation must be conducted (see Section 5.3.2). Subject inclusion and exclusion criteria and withdrawal criteria will exclude subjects deemed to be at risk for increase of QT. Time-matched triplicate digital ECG will be collected at Screening and at multiple time points (predose and postdose [Cmax]) in Cycle 1 and subsequent follow-up ECGs through all cycles. In M4112 monotherapy cohorts only (Part IA only), replicate ECGs (Holter) will also be collected on Days 1 and 15 of Cycle 1 for exposure-QTc analysis. Treatment modification guidance is described in Section 6.2.3.

M4112 is a sensitive substrate to CYP3A4 and it cannot be excluded that it inhibits or induces CYP3A4 to a clinically relevant extent. Strong inhibitors or inducers of CYP3A4 and drugs with a narrow therapeutic index, which are predominantly metabolized by CYP3A4, should be discontinued 7 days prior to treatment and avoided during treatment.

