## **6.5.5 Management of Specific Adverse Events or Adverse Drug Reactions**

Any Grade 4 ADRs require treatment discontinuation except for single laboratory values out of normal range that are unlikely related to study treatment as assessed by the Investigator, do not have any clinical correlate, and resolve within 7 days with adequate medical management.

Any Grade  $\geq 3$  AEs and irAEs require treatment discontinuation with exception of any of ADRs mentioned in Section [6.2.3](#) and [6.2.4](#) in the DLT criteria.

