### 6.5.5.3 Immune-Related Adverse Events

Since inhibition of PD-L1 stimulates the immune system, irAEs may occur. Treatment of irAEs is mainly dependent upon severity (NCI-CTCAE grade):

- Grade 1 to 2: treat symptomatically or with moderate dose steroids, more frequent monitoring
- Grade 1 to 2 (persistent): manage similar to high grade AE (Grade 3 to 4)
- Grade 3 to 4: treat with high dose corticosteroids.

Treatment of irAEs should follow guidelines set forth in [Table 9](#).

**Table 9 Management of Immune-Related Adverse Events of CCI  
M4112 as Single Agent CCI**

Gastrointestinal irAEs		
Severity of Diarrhea/Colitis (NCI-CTCAE 4.03)	Initial Management	Follow-up Management
Grade 1 Diarrhea: < 4 stools/day over Baseline Colitis: asymptomatic	CCI M4112 therapy Symptomatic treatment (eg, loperamide)	Close monitoring for worsening symptoms Educate subject to report worsening immediately If worsens: Treat as Grade 2, 3, or 4
Grade 2 Diarrhea: 4 to 6 stools per day over Baseline; iv fluids indicated < 24 h; not interfering with ADL Colitis: abdominal pain; blood in stool	Delay CCI, or M4112 therapy Symptomatic treatment	If improves to Grade 1: Resume CCI or M4112 therapy  If persists > 5 to 7 days or recurs: Treat as Grade 3 to 4
Grade 3 to 4 Diarrhea (Grade 3): ≥ 7 stools per day over Baseline; incontinence; iv fluids ≥ 24 h; interfering with ADL Colitis (Grade 3): severe abdominal pain, medical intervention indicated, peritoneal signs Grade 4: life-threatening, perforation	Withhold CCI CCI M4112 therapy for Grade 3 Permanently discontinue CCI M4112 therapy for Grade 4 or recurrent Grade 3. 1.0 to 2.0 mg/kg/day prednisone or equivalent Add prophylactic antibiotics for opportunistic infections Consider lower endoscopy	If improves: Continue steroids until Grade 1, then taper over at least 1 month, resume CCI therapy following steroids taper (for initial Grade 3).  If worsens, persists > 3 to 5 days, or recurs after improvement: Add infliximab 5 mg/kg (if no contraindication), Note: Infliximab should not be used in cases of perforation or sepsis Permanently discontinue IMP

Dermatological irAEs		
Grade of Rash (NCI-CTCAE 4.03)	Initial Management	Follow-up Management

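### The DLT exceptions for diarrhea and for nausea and vomiting state no upper grade, so an isolated, short-lived Grade 4 event in Cycle 1 is, read literally, not a DLT

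*Protocol*

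**What the plan says.** Protocol 6.2.4 starts from any Grade ≥ 3 nonhematological AE or irAE in the first 28 days and removes ten kinds of event, (a) to (j). The two at issue are:

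- Diarrhea: at most 6 "days duration following adequate and optimal therapy that resolves to Grade" 1 or lower.
- Nausea and vomiting: at most 72 "h duration with adequate and optimal therapy".

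Three others in the list are limited to Grade 3: "Grade 3 skin toxicity that resolves to Grade 1 or less with supportive measures within 7 days"; "Grade 3 infusion-related reactions resolving within 6 h from the end of infusion and controlled with medical management"; and transient fatigue, fever, headache and similar symptoms. Four state no cap: single laboratory values, keratoacanthoma/SCC, thyroid dysfunction and tumor flare. Asymptomatic lipase or amylase elevation is expressly excepted at Grade ≥ 3.

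Elsewhere Grade 4 is handled more strictly. Protocol 6.5.5 opens with "Any Grade 4 ADRs require treatment discontinuation except for single laboratory values out of normal range that are unlikely related to study treatment", subject to further conditions on those laboratory values. In Table 9 (6.5.5.3), Grade 4 immune-related diarrhea or colitis means permanent discontinuation. These rules govern treatment of the subject; they do not define a DLT. SAP 15.1 refers back to Protocol 6.2.4 for the definition and adds no cap.

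**The concern.** The DLT is the first primary endpoint (Protocol 8.3.1) and the toxicity outcome that the Bayesian model uses to recommend the next dose (8.5.2). Protocol 7.4.1.1 equates Grade 4 with life-threatening. Gastrointestinal intolerance is the first potential risk listed in Protocol 3.4.2.1, which adds: "The symptoms of gastrointestinal intolerance (nausea, vomiting, and diarrhea etc.) will be closely monitored, reported, and investigated". So on the toxicity the sponsor names first, a life-threatening event that resolves quickly could enter the model and the reported DLT rate as a non-event. Because other items in the same list are capped explicitly, sites could also classify the same event differently.

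**Working it through.** **1. Does any other text make the event a DLT?** The committee's discretionary bullet in 6.2.4 covers only a subsequent cycle. The remaining bullets are hematological, QTc-related or hepatic. The lead-in sentence is partly blacked out, but both exceptions are fully legible. No readable text recaptures the event.

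**2. How narrow is the gap?** These remain DLTs: diarrhea lasting more than 6 days or not resolving to Grade ≤ 1, nausea or vomiting beyond 72 h, Grade ≥ 3 colitis, and any accompanying Grade ≥ 3 nonhematological event that is not itself excepted (dehydration or hypotension, for example).

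**3. Model inputs.** Protocol 8.5.2 and SAP Appendix 18.2, section 16.1:

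- logit P(DLT at dose d) = α + exp(β) × log(d/900).
- E(α) = log(0.31/0.69) = −0.8001.
- E(β) = log[(log(0.11/0.89) − log(0.31/0.69)) / log(400/900)] = 0.4647.
- Both SDs 1.5, covariance 0.
- Loss = 1 × P(rate ≤ 0.17) + 0 × P(0.17 to 0.35) + 1 × P(0.35 to 0.67) + 2 × P(> 0.67).
- A dose is eligible only if P(rate > 0.35) < 0.25. The eligible dose with the smallest loss is recommended.

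**4. Reproducing the plan's figures.** Integrating the posterior on a 1601 × 1601 grid returns the recommended dose in every Appendix V scenario, 1 to 6b. For example:

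- Scenario 1 (0/3 at 100 mg) gives 600 mg, where P(rate > 0.35) = 0.12 + 0.02 = 0.14.
- Scenario 1a (1/3 at 100 mg) gives 100 mg, where P(rate > 0.35) = 0.22 + 0.02 = 0.24, only just eligible.

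**5. One event, counted or not.** Cohort of 3, all lower cohorts 0/3. The last two columns give P(DLT rate > 35%) at the next planned dose.

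| Current dose | Recommended, not counted (0/3) | Recommended, counted (1/3) | Next planned dose | P, not counted | P, counted |
|---|---|---|---|---|---|
| 100 mg | 600 mg | 100 mg | 200 mg | 0.027 | 0.356 |
| 200 mg | 800 mg | 200 mg | 400 mg | 0.029 | 0.268 |
| 400 mg | 800 mg | 400 mg | 600 mg | 0.041 | 0.268 |
| 600 mg | 800 mg | 600 mg | 800 mg | 0.094 | 0.341 |
| 800 mg | 900 mg | 800 mg | 900 mg | 0.154 | 0.376 |

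Not counted, all five next steps pass the 25% limit; counted, all five fail. After 900 mg the recommendation stays at 900 mg either way.

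**6. If the subject leaves the analysis set.** A related Grade 4 event stops treatment under 6.5.5. Protocol Table 13 excludes subjects who miss more than 5 total daily doses for a reason other than a DLT, while 6.2.4 excludes them only if the reason is not safety. Under Table 13 the uncounted case may therefore be 0/2. The recommended doses are the same as for 0/3, and the next-step probabilities become about 0.04, 0.04, 0.05, 0.11 and 0.18. All still pass.

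**7. Larger cohorts.** The effect fades. With 1/4 counted, 3 of the 5 next steps fail; with 1/5, 2 of 5; with 1/6, none (0.149 to 0.235). In a cohort of 6 the recommendation is still lower when the event is counted after 100 to 600 mg: 200 against 800, 400 against 800, 600 against 800, and 800 against 900 mg. The planned cohort size is 3.

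**The case against.** The strongest reply is that the list is not built on a Grade 3 cap. Only three of ten exceptions carry one, four others have none, and lipase/amylase expressly reaches higher grades, so the missing caps may be deliberate. That stands as a caution: the documents do not show an oversight. It does not make the literal result a good one for a life-threatening event on a named risk.

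The scenario is also rare. Life-threatening diarrhea or vomiting without any other non-excepted Grade ≥ 3 event will be unusual, the documents give no probability, and Protocol 8.1 expects few DLTs. The table shows what one uncounted DLT does to the model; it does not show how often this gap would operate.

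A reader might infer that the event would go unseen or that escalation would follow automatically. The documents do not support either. The event must be reported as an SAE (7.4.1.1), within 24 h (7.4.1.4), and it counts in the TEAE endpoint. The committee gets current-cohort patient profiles with all serious and nonserious events (SAP Appendix 18.2, 16.1) and adverse event listings at the current cut-off (17.1.1). Protocol 3.4.2.1 recommends interruption or discontinuation for Grade ≥ 3 gastrointestinal events, and 8.5.2 lets the committee depart from the model. These safeguards rest on judgment, and they leave the posterior and the reported DLT rate unchanged.

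A reader might also infer that 6.5.5 needs rewriting, because its second sentence says that Grade ≥ 3 "AEs and irAEs require treatment discontinuation with exception of any of ADRs mentioned in Section" 6.2.3 and 6.2.4, without saying whether this yields to the Grade 4 rule. Making the Grade 4 rule dominant would conflict with 6.2.3, which lets a subject with a Grade 4 hematological reaction after Cycle 1 resume at a reduced dose, and with Table 9, which lets Grade 4 endocrinopathies be withheld and resumed. It is not needed to close this gap.

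**Conclusion.** The point holds as a wording gap worth fixing. As written, an isolated Grade 4 diarrhea event of at most 6 days that resolves to Grade ≤ 1, or Grade 4 vomiting of at most 72 h, is not a DLT in Cycle 1.

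Conditional on one such event in a cohort of 3 with all lower cohorts 0/3, P(DLT rate > 35%) at the next planned step is 0.03 to 0.15 if it is not counted (0.04 to 0.18 if the subject drops out of the Dose Escalation set) and 0.27 to 0.38 if it is. The classification therefore decides whether the 25% rule allows the next step from each dose between 100 and 800 mg.

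This rests on the literal reading, on the readable text (part of the 6.2.4 lead-in is blacked out), and on the protocol's prior and loss function. Nothing in the documents shows that such an event occurred or that any dose decision in Part IA was affected.

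**What to change.** In Protocol 6.2.4, put Grade 3 in front of the two exceptions: Grade 3 diarrhea of ≤ 6 days duration, and Grade 3 nausea and vomiting of ≤ 72 h duration, with the rest of each line unchanged. Leave the other exceptions, 6.5.5 and Table 9 as they are.

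The cost is a short amendment with no new data collection. A few more events may count as DLTs, which would slow escalation and end protocol treatment for those subjects. Because 6.2.3 borrows the DLT exceptions for its interruption rule after Cycle 1, the cap would apply there too. The change helps only if made before escalation; SAP section 7 reports that Part IA is complete and that the combination parts never opened, so for this study it serves mainly as a template correction.

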### 6.3 Assignment to Treatment Groups

Once the subject has provided a signed ICF and meets all inclusion criteria and does not meet any exclusion criterion, subjects will be assigned to receive open-label M4112 as a single agent, **CCI**

Subjects will be assigned sequentially to cohorts of either M4112 as a single agent, **CCI**. During dose-escalation, the SMC may decide (based on available data) upon enrollment and dose for the next dosing cohort before all subjects in a cohort have completed Cycle 1.

Subject identifiers will comprise 17 digits, the first 10 digits representing the study number, the following 3 digits representing the site number, and the last 4 digits representing the subject number, which is allocated sequentially starting with **PPD**.

### 6.4 Noninvestigational Medicinal Products to be Used

[figure not shown]
Storage, handling, preparation, and disposal of commercially sourced non IMPs should occur according to the package insert specifications and local institutional guidelines.

The investigator is responsible for ensuring accountability for non IMPs, including reconciliation of drugs and maintenance of drug records in the same manner as described for IMPs in Section 6.8.

Immediate access to an intensive care unit or equivalent environment and appropriate medical therapy (including epinephrine, corticosteroids, intravenous antihistamines, bronchodilators, and oxygen) must be available for use in the treatment of infusion-related reactions **CCI**

[figure not shown]
As with all monoclonal antibody therapies, there is a risk of hypersensitivity reaction. Patients should be monitored for signs/symptoms of infusion reactions including but not limited to pyrexia, chills, flushing, hypotension, dyspnea, wheezing, back pain, abdominal pain, and urticaria. Interruption or slow the rate of infusion for mild or moderate infusion-related reactions.

CCI

[figure not shown]

If hypersensitivity reaction occurs, the subject must be treated according to the best available medical practice. Guidelines for management of infusion-related reactions and severe hypersensitivity and flu-like symptoms according to the NCI are found in Sections 6.5.5.1 and 6.5.5.2, respectively. A complete guideline for the emergency treatment of anaphylactic reactions according to the Working Group of the Resuscitation Council (United Kingdom) can be found at <https://www.resus.org.uk/pages/reaction.pdf>. Subjects should be instructed to report any delayed reactions to the Investigator immediately.

CCI

CCI

## 6.5 Concomitant Medications and Therapies

All concomitant medications taken by the subject during the study, from the date of signature of informed consent are to be recorded in the appropriate section of the eCRF, noting the name, dose, duration and indication of each drug. Nondrug interventions and any changes to a concomitant medication or other intervention should also be recorded in the eCRF.

### 6.5.1 Permitted Medicines

Any medications, therapies or procedures (other than those excluded by the clinical study protocol) that are considered necessary for the subjects' welfare according to local standard of

care and will not interfere with **CCI**  
[REDACTED] may be given at the Investigator's discretion.

Other drugs to be used for prophylaxis, treatment of hypersensitivity reactions, and treatment of fever or flu-like symptoms are described in Section [6.5.5.2](#).

Hematopoietic growth factors can be used if medically indicated according to standard of care only after the DLT period of 28 days.

Erythropoietin and darbepoetin-alpha are permitted outside the DLT window. Hormonal therapies acting on the hypothalamic-pituitary-gonadal axis are permitted (ie, luteinizing hormone-releasing hormone agonist/antagonists). No other hormonal anticancer therapy is permitted.

Rescue medications may be administered due to anticipated adverse reactions or anticipated emergency situations.

Administration of corticosteroids through a route known to result in a minimal systemic exposure (topical, intranasal, intra-ocular, or inhalation) and anti-infectious drugs are permitted.

## 6.5.2 Prohibited Medicines

Prohibited medicines are indicated in the exclusion criteria (see Section [5.3.2](#)).

During the study, any other investigational drug, chemotherapy, extensive radiotherapy (involving  $\geq 30\%$  of bone marrow) or any other anticancer therapy (cytotoxics, biologics or other targeted therapy) are prohibited.

In vitro assessments indicate that M4112 is a sensitive substrate to CYP3A4 and cannot exclude that it can inhibit or induce CYP3A4 at a clinically relevant extent. Strong inhibitors or inducers of CYP3A4, and drugs with a narrow therapeutic index, which are predominantly metabolized by CYP3A4 should be discontinued 7 days prior to treatment and avoided during treatment. **CCI**  
[REDACTED] An

updated list of nonpermitted drugs can be accessed via the following link:

<http://www.fda.gov/Drugs/DevelopmentApprovalProcess/DevelopmentResources/DrugInteractionsLabeling/ucm093664>

Drugs known to have a high risk to prolong QTc as per label or Credible Meds web site (formerly AZCert) are prohibited. For antihistamines only drugs with high risk of QTc prolongation (in the label) or risk mentioned in the label are prohibited (Diphenhydramine is considered of low risk and can be used)

Corticosteroids and immunesuppressants given systemically at therapeutic doses are not permitted throughout treatment other than for treatment of immune-related adverse events and for endocrine replacement therapy (equivalent to  $< 10$  mg prednisone daily).

Concomitant use of warfarin or other Vitamin K antagonists is also prohibited.

The solubility of M4112 is pH dependent; therefore, co-administration of antacid drugs, H2-blocker and proton pump inhibitors (PPIs) are likely to decrease the absorption of M4112. H2-blockers or PPIs should be stopped 5 days prior to the first treatment, and avoided during the entire treatment period with IMP. Antacid drugs should not be taken 1 h before IMP administration until 2 h after IMP administration.

The following treatments must not be administered during the study:

- Immunotherapy including interferon, immunosuppressive drugs (eg, chemotherapy or systemic corticosteroids except for short term treatment of allergic reactions, endocrine replacement therapy at low dose prednisone [ $\leq 10$  mg daily] or equivalent, or for the treatment of irAEs or other appropriate short term steroid use), or other experimental pharmaceutical products. Short term administration of systemic steroid or other immunosuppressant such as infliximab or mycophenolate (ie, for allergic reactions or the management of irAEs) is allowed. Steroids with no or minimal systemic effect (topical, inhalation) are allowed.  
Note: for subjects with glioblastoma, steroid use is allowed

- Adefovir
- Prophylactic use of corticosteroids for infusion related reactions is prohibited
- Any live vaccine therapies for the prevention of infectious disease within 28 days prior to study entry and during study. Administration of inactivated vaccines is allowed (eg, inactivated influenza vaccines)
- Blood transfusions and erythroid growth factors are not allowed during the 28-day DLT window during the escalation phase. These subjects are considered to have had a DLT if the drop in hemoglobin is rated as drug related, or subjects are regarded as not evaluable, if the event is not related to study medication.

If the administration of a nonpermitted concomitant drug becomes necessary during the study, the subject will be withdrawn from study treatment (the Medical Monitor should be contacted to discuss whether the IMP must be discontinued).

[figure not shown]
